#### **4.2.2 Maintaining Similar Levels of Follow-up**

To maintain similar levels of contact between the investigational site and subjects, all subjects will have a "Treatment" visit. During the "Treatment" visit for the Control group, subjects will be

Study Document No: ABT-CIP-10249

Study Name: TRILUMINATE Pivotal

**CONFIDENTIAL:** May not be reproduced outside of Abbott without written permission from Document Control. This is a quality record which will be retained per the local retention policy.

## **TRILUMINATE Pivotal CIP** (Version F)

seen by a HF specialist, and will undergo a physical exam, including vital signs, cardiac health status and evaluation of heart failure medications. Subjects in the Device group will undergo the TriClip™ procedure during the “Treatment” visit.

### **4.2.3 Administration of Assessments**

Site personnel assessing NYHA Functional Class, administering the 6MWT and QoL questionnaires during the follow up visits (30-day visit and afterwards) will be blinded to the subject’s treatment assignment and will not be involved in day-to-day activities of the TRILUMINATE Pivotal trial. Additionally, personnel performing these assessments will not have access to the electronic case report forms (eCRFs). A standardized script will be used when administering the assessments and the subject will be reminded to not reveal their treatment history to the administrator. To minimize bias and undue influence, the QoL questionnaires will be completed by the subject, unless the subject is unable to complete the questionnaire on their own (in such cases, a note to file must be completed to document the inability of subject to complete the questionnaire).

### **4.2.4 Eligibility Committee (EC)**

An independent EC will comprise, at a minimum, representatives from the following specialties: heart failure specialist, interventional cardiologist and echocardiologist. The EC will determine if the subject is being managed according to optimized medical therapy, evaluate the clippability of the tricuspid valve and determine whether the subject will be enrolled in the Randomized or Single-arm cohort. Review will be performed via teleconference with presentation (i.e. Webex) or other formats on a regular basis (i.e. weekly) between the EC, ECL representative, and a study site(s) representative(s) of the proposed subject(s). The composition, guiding policies, and operating procedures governing the EC are described separately in the charter.

### **4.2.5 Review of Echocardiography Images**

TR severity and other echocardiographic measurements will be assessed by an independent ECL at screening, baseline and follow-up. Prior to enrollment, the ECL will confirm subject’s screening echocardiography images for TR severity per the guideline for TR grading (defined in **Appendix XII**). Finally, the ECL will be responsible for assessing TR severity and echocardiographic analyses at all visits (baseline and follow-ups).

### **4.2.6 Safety and Effectiveness Monitoring**

- All adverse events will be reviewed by Abbott Clinical Safety team.
- Adverse events requiring adjudication will be submitted to an independent CEC. See section 11.7.4.
- A Data Monitoring Committee (DMC) will review accumulating safety and effectiveness data as described in Section 11.7.3.

### **4.2.7 Follow-Up Compliance**

The Sponsor will work with investigational sites to maintain high follow-up compliance. The following are strategies for increasing compliance:

- During the site initiation visit, the Sponsor will emphasize to the site the importance of subject follow-up, and that the site should communicate this importance to each subject.

## **TRILUMINATE Pivotal CIP** (Version F)

- Sites should promptly reschedule any missed subject visits, and to reinforce the necessity of a follow-up visit to subjects.
- If a scheduled visit is missed due to subject illness, transportation issues, or travel, the site should:
  - Reinforce the necessity of follow-up visits;
  - Identify alternate transportation sources, and involve the Sponsor if necessary.
- Sites will be instructed to ask subjects who withdraw during the trial to provide the reason for withdrawal and ask them if the investigator may contact them to check their vital status at the end of the trial follow-up.
- Follow-up rates will be monitored closely so follow-up problems may be identified and addressed as soon as possible.
- For subjects lost-to-follow-up, sites may be requested to examine the Social Security Death Index to determine subject status (only the status will be sent to Sponsor, not any subject identifying information).

In addition to aforementioned steps, investigational sites will be educated on the importance of maintaining low rates of withdrawals in both Device and Control groups, and will be expected to make all efforts to maintain low withdrawals during trial conduct. If necessary, an independent service (e.g. Hawthorne Effect) may be utilized to provide in-home visits to aid in follow-up compliance. Withdrawals from the trial may need discussion between investigator and the Sponsor.

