## **5 ENDPOINTS**

### **5.1 Randomized Cohort**

#### **5.1.1 Primary Endpoint**

The primary endpoint is a hierarchical composite of all-cause mortality or tricuspid valve surgery, heart failure hospitalizations, and quality of life improvement assessed using the KCCQ at 12 months. The endpoint will be evaluated in a hierarchical order as follows:

- Time to all-cause death or tricuspid valve surgery
- Number of Heart Failure (HF) Hospitalizations
- An Improvement of  $\geq 15$  points in KCCQ from baseline

HF Hospitalization includes any of the following:

1) Hospitalization ( $\geq 24$  hours) with the primary reason for admission as acute decompensated HF and administration of intravenous or mechanical heart failure therapies, especially IV administration of diuretic therapy.

2) An unscheduled or unplanned admission to the emergency department, hospital outpatient observation unit, or hospital inpatient unit, and IV administration of diuretic therapy. Overnight stays for IV administration of diuretic therapy at nursing home facilities, physical rehab or extended care facilities, including hospice, will be included in the definition of hospitalization if related to heart failure.

3) Subject arrives in emergency department with clinical presentation meeting the criteria of HF, but dies in the emergency department before hospital admission.

Elective heart failure “tune-ups” that occur following the TriClip™ procedure and prolong hospitalization will not count as a heart failure hospitalization.

Based on the current experience, it is expected that the Device group may experience a mortality benefit, improved freedom from heart failure symptoms, as well as a quality of life improvement when their TR is treated.

Study Document No: ABT-CIP-10249

Study Name: TRILUMINATE Pivotal

**CONFIDENTIAL:** May not be reproduced outside of Abbott without written permission from Document Control. This is a quality record which will be retained per the local retention policy.

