## **6.5 Subject Withdrawal**

Each enrolled subject shall remain in the clinical investigation until completion of the required follow-up period; however, a subject's participation in any clinical investigation is voluntary and the subject has the right to withdraw at any time without penalty or loss of benefit. Conceivable reasons for discontinuation may include, but not be limited to, the following:

- Subject death
- Subject voluntary withdrawal
- Subject lost-to follow-up as described below

The Sponsor must be notified of the reason(s) for subject discontinuation. The site will provide this information to the Sponsor. Investigators must also report this to their respective IRB/EC as defined by their institution's procedure(s).

No additional follow-up will be required or data recorded from subjects once withdrawn from the clinical investigation, except for the status (deceased/alive).

However, if a subject withdraws from the investigation due to problems related to the safety or performance of the device under investigation, the investigator shall ask for the subject's permission to follow his/her status/condition outside of the clinical investigation.

In case of subject withdrawal, the site should make attempts to schedule the subject for a final clinical investigation visit. At this final follow-up visit, the subject will undergo the following assessments:

- 12-lead ECG
- Blood draw (Same as required for follow-up visits)
- Physical exam including vital signs (weight, heart rate and blood pressure)
- Echocardiogram – TTE
- Modified Rankin Scale (Assessment of mRS should be done only after onset of stroke; not required after 12 months)
- 6-Minute Walk Test (6MWT) – See **APPENDIX XIII** for 6 Minute Walk Test Guidelines
- Concomitant cardiovascular medications assessment
- NYHA Functional Class assessment
- KCCQ QoL questionnaire to be completed by the subject – must be administered by “blinded” study personnel. Note: To minimize bias and undue influence, the QoL questionnaires will be completed by the subject, unless the subject is unable to

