### Lost-to-Follow-up

If the subject misses two consecutive scheduled follow-up time points and the attempts at contacting the subject detailed below are unsuccessful, then the subject is considered lost-to-follow-up. Site personnel shall make all reasonable efforts to locate and communicate with the subject (and document these efforts in the source documents), including the following, at each contact time point:

- A minimum of three telephone calls over a period of 10 days to contact the subject or his/her relative/caregiver (where allowed per local regulations) should be recorded in the source documentation, including date, time and initials of site personnel trying to make contact.
- If these attempts are unsuccessful, a letter (certified if applicable) should be sent to the subject. The registered letter will request the subject to contact the site.
- If the above attempts are unsuccessful, the patient's general practitioner shall be contacted to investigate about the subject's whereabouts and his/her health status (where allowed per local regulations).

If a subject misses one or more non-consecutive follow-up contact time points, it will be considered a missed visit. The subject may then return for subsequent visits. If the subject misses two consecutive time points and the above-mentioned attempts at communicating with the subject are unsuccessful, the subject will be considered lost-to-follow-up.

Note: Telephone contact with General Practitioner, non-clinical investigation cardiologist or relative without the presence of the subject or indirect documentation obtained via discharge letters will not be considered as subject contact.

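### Capture of year-one deaths after withdrawal in tier 1 of the primary endpoint is not assured: no visible rule requires a dated vital-status check before the 12-month analysis

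*Protocol*

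**What the plan says.** Collection after withdrawal:

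- Protocol 4.2.7 (Follow-Up Compliance): sites ask a withdrawing subject for the reason and "ask them if the investigator may contact them to check their vital status at the end of the trial follow-up". Protocol 4.1 sets follow-up at five years per subject.
- Protocol 6.5 (Subject Withdrawal): "No additional follow-up will be required or data recorded from subjects once withdrawn from the clinical investigation, except for the status (deceased/alive". No time is given for obtaining that status, and a date of death is not mentioned. On withdrawal, "the site should make attempts to schedule the subject for a final clinical investigation visit". If the withdrawal concerns device safety or performance, permission is sought to follow the subject outside the trial.
- Protocol 8.3.1: safety reporting, deaths included, stops when the subject withdraws.

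A separate route covers subjects lost to follow-up. Sites may be asked to search the Social Security Death Index, and "only the status will be sent to Sponsor, not any subject identifying information" (Protocol 4.2.7). A subject counts as lost "If the subject misses two consecutive scheduled follow-up time points and the attempts at contacting the subject detailed below are unsuccessful" (Protocol 6.5, Lost-to-Follow-up).

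Use of the data: tier 1 of the primary endpoint is "Time to all-cause death or tricuspid valve surgery" (Protocol 5.1.1). It is analysed in the ITT population by the Finkelstein-Schoenfeld method (SAP 2.3.1.1), once 350 subjects have 12 months of follow-up or later if the sample size is increased (SAP 2.6.1). All-cause mortality is also part of a 24-month secondary endpoint. SAP 2.2.3 censors event-free subjects in time-to-event analyses at the last event-free time known while they remain in the study.

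**The concern.** The collection rules and the analysis do not share a timetable. Tier 1 needs to know who died within 12 months and when. For withdrawn subjects, the text sets a time for one status check, years after that analysis, and asks for a yes/no answer. A site could follow the plan exactly and have no dated death to report at the 12-month or 24-month lock.

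Death heads the hierarchy and is the outcome least open to reporting bias in a trial whose subjects know their assignment (Protocol 4.2). Control subjects may not receive the device before the 12-month visit (Protocol 7.11), so unequal withdrawal between the arms is plausible, although no document figure shows it. If the arms leave at different rates and those who leave have a different risk of death, dropping their later deaths could distort the comparison as well as lose information.

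**Working it through.** **The plan's own figure.** SAP 2.4.1.1 states about 83% power with 350 subjects at two-sided 5%. It cannot be reproduced, because the component rates and attrition assumptions are redacted.

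**Timeline from the visible text**

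- Withdrawal in year one: adverse event and death reporting ends (Protocol 8.3.1).
- Month 12: primary analysis, tier 1 being a time to event.
- Month 24: mortality secondary.
- Year 5: the stated vital-status contact, if the subject agreed to it.

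**Expected deaths after withdrawal in year one**

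Inputs: N = 350 (SAP 2.4.1.1); share withdrawing in year one, w = 3% to 10% (assumed); one-year mortality, q = 10% to 25% (assumed). Withdrawal time u is uniform over the year, the hazard is constant at λ = −ln(1 − q), and each subject is alive at withdrawal.

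A subject who leaves at time u dies in the rest of the year with probability 1 − exp(−λ(1 − u)). Averaged over u, this is 1 − q/λ. Expected deaths are N × w × (1 − q/λ).

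- Low end: λ = 0.1054; 1 − 0.10/0.1054 = 0.0509; 350 × 0.03 × 0.0509 = 0.53.
- High end: λ = 0.2877; 1 − 0.25/0.2877 = 0.1310; 350 × 0.10 × 0.1310 = 4.58.

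The range is about 0.5 to 4.6 deaths. Against total year-one deaths of N × q, that is 0.53/35 = 1.5% at the low end and 4.58/87.5 = 5.2% at the high end.

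If the hazard doubles after withdrawal, the average becomes 1 − (1 − (1 − q)²)/(2λ):

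- Low end: 1 − 0.19/0.2107 = 0.0983; × 10.5 = 1.0.
- High end: 1 − 0.4375/0.5754 = 0.2396; × 35 = 8.4.

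**Share of comparisons.** With 175 per arm there are 175 × 175 = 30,625 Device-Control pairs, and each subject is in 175 of them (0.57%). So 4.6 deaths touch at most about 2.6% of pairs. Pairs already decided before the withdrawal would not change.

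**Power and bias, illustrative only.** A Finkelstein-Schoenfeld simulation used 600 runs per scenario and assumed Control and Device values of 20% and 15% for death, 0.70 and 0.50 heart failure hospitalizations per year, and 25% and 36% KCCQ responders. It is not calibrated to the plan's 83%. Power with no withdrawal was 0.69.

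| Withdrawal | Hazard after withdrawal | Later deaths not captured | Later deaths captured |
|---|---|---|---|
| 5% | unchanged | 0.67 | 0.66 |
| 10% | unchanged | 0.67 | 0.62 |
| 10% | doubled | 0.65 | 0.64 |

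Each power carries a standard error of about √(0.65 × 0.35/600) = 0.02, so no difference is clear.

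In one run with no treatment effect, withdrawal was 12% in Control and 3% in Device, with the hazard doubled after withdrawal. The rejection rate was 0.03 without capture and 0.05 with it, and the mean test statistic was −0.03 and 0.10. That run shows no inflation of type I error.

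**The case against.** The strongest reply is that the documents leave room for proper ascertainment and that much of the governing text cannot be seen. Several stronger readings are tempting and are not supported:

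- **That status is checked only at the end of follow-up.** The word "only" is not in 4.2.7, which lists compliance strategies. Section 6.5 keeps status after withdrawal and sets no time, so an earlier check is allowed.
- **That no date is kept.** Section 6.5 is silent on a date and does not prohibit one. The death-index sentence concerns subjects lost to follow-up, and it contrasts status with identifying information, so it reads as a privacy clause. A Death Form exists (Protocol 7.13), but its fields are not shown.
- **That these deaths cannot enter tier 1.** The ITT definition, the pair-comparison rules, the missing-data sections and part of the sensitivity analyses are redacted. No visible rule bars a dated death found before the lock.
- **That a subject who first misses month 12 falls into the same gap.** That subject has not withdrawn. Section 6.5 calls for telephone calls, a letter and general-practitioner contact at each contact time point, and safety reporting continues. Only the optional index search waits for a second missed visit.
- **That up to about nine deaths are lost.** Multiplying 350 × 10% × 25% = 8.75 charges each withdrawn subject a full year of mortality, although each was alive on leaving and had only the rest of the year at risk.

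What survives is narrower. The collection rules in 4.2.7, 6.5 and 8.3.1 are visible, and no redacted analysis rule can rank a death date that was never collected. The attempted final visit shows only that the subject was alive then. Following a device-related withdrawal outside the trial does not by itself put dated data into it.

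**Conclusion.** The concern holds as a gap in assurance. For withdrawn subjects, the visible text does not require a vital-status check before the 12-month or 24-month analysis, or a date of death, and it ends routine death reporting at withdrawal. Their year-one deaths may therefore be missing from tier 1, and later ones from the 24-month mortality secondary.

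The size is small to modest: about 0.5 to 4.6 deaths among 350, or 1.5% to 5.2% of year-one deaths, rising to 1.0 to 8.4 deaths if the hazard doubles after withdrawal. These figures rest on assumed withdrawal of 3-10%, assumed mortality of 10-25% and withdrawal spread evenly over the year; the documents give none of these. No clear loss of power was shown, and bias from unequal withdrawal is possible but not demonstrated. The case for a change is completeness of the leading component at low cost, and it does not put the primary analysis as a whole in doubt.

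**What to change.** - **Protocol 4.2.7 and 6.5:** replace the end-of-follow-up contact with a vital-status check completed before the 12-month database lock, before the 24-month lock, and at five years, where consent and law allow.
- **Data:** record the date of death or the date last known alive, with the source.
- **Registry search:** allow it for any subject whose status is unknown at a lock, not only for those formally lost to follow-up.
- **SAP:** state that a dated death after withdrawal counts in tier 1 and is not censored at withdrawal. Without this the new dates might go unused, because SAP 2.2.3 points to censoring when a subject leaves the study.

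The cost is protocol and consent wording, one date field, and a short status check by sites before two locks. No visits or subjects are added. The check recovers deaths only; tricuspid valve surgery after withdrawal, the other part of tier 1, would remain uncollected.

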### **4.3 Continued Access Study Procedures and Follow-up Schedule**

Following the completion of enrollment in both the randomized and single-arm cohorts of the TRILUMINATE Pivotal trial, subjects from eligible sites will be enrolled into a continued access study. Details of the continued access study procedures and follow-up schedule are included in Appendix XVI.

### **4.4 Suspension or Early Termination of the Clinical Investigation**

No formal statistical rule for early termination of the clinical investigation for insufficient effectiveness of the device under investigation is defined.

The Sponsor reserves the right to discontinue the clinical investigation at any stage or reduce the follow-up period with suitable written notice to the investigator. Possible reason(s) may include, but are not limited to:

- Unanticipated adverse device effect (e.g., UADE) occurs and it presents an unreasonable risk to the participating subjects
- Any oversight committee (e.g., Steering Committee, Data Monitoring Committee) makes a recommendation to stop or terminate the clinical investigation (such as higher frequency of anticipated adverse device effects)
- Further product development is cancelled

Should the clinical investigation be discontinued by the Sponsor, subjects will be followed per routine hospital practice with device-related AEs reported to the Sponsor as per vigilance/commercial reporting requirements.

**TRILUMINATE Pivotal CIP**  
(Version F)

Should early termination occur, the investigator shall return all clinical investigation materials (including devices) to the Sponsor, and provide a written statement as to why the premature termination has taken place to the IRB/EC (if applicable). All applicable clinical investigation documents shall be subject to the same retention policy as detailed in Section 12.5 of the CIP. A Principal Investigator, IRB/EC or regulatory authority may suspend or prematurely terminate participation in a clinical investigation at the investigational sites for which they are responsible. The investigators will follow the requirements specified in the Clinical Trial Agreement.

If the Sponsor suspends or prematurely terminates the clinical investigation at an individual site in the interest of safety, the Sponsor will inform all other Principal Investigators.

If suspension or premature termination occurs, the Sponsor will remain responsible for providing resources to fulfill the obligations from the CIP and existing agreements for following the subjects enrolled in the clinical investigation, and the Principal Investigator or authorized designee will promptly inform the enrolled subjects at his/her site, if appropriate. Additionally, an effort will be made to hasten the release of results if the study is terminated early.

## **5 ENDPOINTS**

### **5.1 Randomized Cohort**

#### **5.1.1 Primary Endpoint**

The primary endpoint is a hierarchical composite of all-cause mortality or tricuspid valve surgery, heart failure hospitalizations, and quality of life improvement assessed using the KCCQ at 12 months. The endpoint will be evaluated in a hierarchical order as follows:

- Time to all-cause death or tricuspid valve surgery
- Number of Heart Failure (HF) Hospitalizations
- An Improvement of  $\geq 15$  points in KCCQ from baseline

HF Hospitalization includes any of the following:

1) Hospitalization ( $\geq 24$  hours) with the primary reason for admission as acute decompensated HF and administration of intravenous or mechanical heart failure therapies, especially IV administration of diuretic therapy.

2) An unscheduled or unplanned admission to the emergency department, hospital outpatient observation unit, or hospital inpatient unit, and IV administration of diuretic therapy. Overnight stays for IV administration of diuretic therapy at nursing home facilities, physical rehab or extended care facilities, including hospice, will be included in the definition of hospitalization if related to heart failure.

3) Subject arrives in emergency department with clinical presentation meeting the criteria of HF, but dies in the emergency department before hospital admission.

Elective heart failure “tune-ups” that occur following the TriClip™ procedure and prolong hospitalization will not count as a heart failure hospitalization.

Based on the current experience, it is expected that the Device group may experience a mortality benefit, improved freedom from heart failure symptoms, as well as a quality of life improvement when their TR is treated.

Study Document No: ABT-CIP-10249

Study Name: TRILUMINATE Pivotal

**CONFIDENTIAL:** May not be reproduced outside of Abbott without written permission from Document Control. This is a quality record which will be retained per the local retention policy.

